4. PLANNED ANALYSES

The following analyses will be performed for this study:

- Final analysis

4.1. DATA MONITORING COMMITTEE (DMC)

There will be no planned DMC for this study.

4.2. INTERIM ANALYSIS

No interim analysis is planned for this study.

4.3. FINAL ANALYSIS

The final, planned analysis identified in this SAP will be performed by IQVIA Biostatistics following Sunovion authorization of this SAP, Sunovion authorization of analysis populations, and database lock.

5. ANALYSIS POPULATIONS

Agreement and authorization of subjects included/excluded from each analysis population will be conducted prior to database lock of the study.

5.1. SAFETY POPULATION

The safety population includes all subjects who were enrolled and received at least one dose of study drug

Document: Documentation\SAP

Author:

Version Number:

Final V1.0

Version Date:

27FEB2019

Template No: CS_TP_BS016 Revision 4
 Effective Date: 01Apr2016

Reference: CS_WI_BS005

Copyright © 2009, 2010, 2012, 2016 Quintiles Transnational Corp. All rights reserved.

The contents of this document are confidential and proprietary to Quintiles Transnational Corp. Unauthorized use, disclosure or reproduction is strictly prohibited.

during the 26-week open-label extension period.

The safety population will be used for the long-term safety, tolerability, and efficacy analyses.

5.2. RELAPSE POPULATION

The relapse population will include safety population subjects who demonstrated a clinical response to 4 weeks of treatment with SEP-363856. Clinical response is defined as meeting both of the following criteria:

- A decrease in PANSS total score of $\geq 20\%$ from baseline
- A CGI-S score ≤ 4

For subjects who received double-blind SEP-363856 in study 361-201, clinical response will be evaluated using the Week 4 (Visit 7) PANSS and CGI-S data of study 361-201, against the double-blind baseline (see section 6.2). For subjects who received double-blind placebo, clinical response will be evaluated using the Week 4 (Visit 5E) PANSS and CGI-S data of study 361-202, against the double-blind baseline (see section 6.2).

The relapse population will be used for analysis of relapse of psychotic symptoms.

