15.3.6.8. Rate of Relapse and Time to Relapse

The relapse will be assessed in subjects who demonstrated clinical response to 4 weeks of treatment with SEP-363856. Clinical response is defined as meeting both of the following criteria:

- 1) a decrease in PANSS total score of $\geq 20\%$ from baseline, and
- 2) a CGI-S score ≤ 4 .

For subjects assigned to double-blind SEP-363856, clinical response will be evaluated using the Day 29 data of study SEP361-201, against the DB baseline of study SEP361-201. For subjects assigned to double-blind placebo, clinical response will be evaluated using the Day 29 data of study SEP361-202, against the OL baseline of study SEP361-202.

Relapse will be identified programmatically using the pre-defined criteria ([Section 6.2](#)) among subjects who demonstrated a clinical response to 4 weeks of treatment with SEP-363856. The rate of relapse will be calculated as the proportion of subjects with a relapse in the 26-week open-label extension period out of all subjects who demonstrated clinical response, along with the 95% confidence interval. The time-to-relapse will be summarized descriptively and will also be presented by a Kaplan-Meier plot.

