Study Visit Number Study Visit Week	Visit1E ^a Baseline	Visit2E Week 1	Visit3E Week 2	Visit4E Week 3	Visit5E Week 4	Visit6E Week 8	Visit7E Week 12	Visit8E Week 16	Visit9E Week 20	Visit10E Week 24	Visit 11E Week 26 or ET ^b	Visit 12E Week 27 Follow- up ^c EOS	
Study Visit Day	1	8 ± 2	15 ± 2	22 ± 2	29 ± 3	57 ± 3	85 ± 3	113 ± 3	141 ± 3	169 ± 3	183 ± 3	190 ± 2	
Brief Negative Symptoms Scale (BNSS)	↓	X	X	X	X	X	X	X	X	X	X		
Clinical Global Impression – Severity (CGI-S)		X	X	X	X	X	X	X	X	X	X	X	
Montgomery-Asberg Depression Rating Scale (MADRS)		X	X	X	X	X	X	X	X	X	X	X	
Columbia Suicide Severity Rating Scale (C-SSRS)		X	X	X	X	X	X	X	X	X	X	X	X
Drug effects questionnaire (DEQ)												X	X
Abnormal Involuntary Movement Scale (AIMS) ¹		X	X	X	X	X	X	X	X	X	X	X	
Barnes Akathisia Rating Scale (BARS) ¹		X	X	X	X	X	X	X	X	X	X	X	
Simpson-Angus Scale (SAS) ¹		X	X	X	X	X	X	X	X	X	X	X	
Pittsburg Sleep Quality Index (PSQI)		X				X		X			X	X	X
Cogstate Cognition Battery (CBB)													
Cogstate Schizophrenia Battery (CSB)								X				X	
USPA-B	X						X				X		

Abbreviations: AE = adverse event; AIMS = Abnormal Involuntary Movement Scale; BARS = Barnes Akathisia Rating Scale; β-hCG = human chorionic gonadotropin; BNSS = Brief Negative Symptoms Scale; CGI-S = Clinical Global Impression – Severity; CBB = Cogstate Brief Battery; CSB = CogState Schizophrenia Battery; C-SSRS = Columbia Suicide Severity Rating Scale ; ECG = Electrocardiogram; ET = early termination; MADRS = Asberg Depression Rating Scale; SAS = Simpson-Angus Scale; PANSS = Positive and Negative Syndrome Scale; PK = pharmacokinetic; PSQI = Pittsburg Sleep Quality Index;

Document: Documentation\SAP
 Author:

Version Number:
 Version Date:

Final V1.0
 27FEB2019

Template No: CS_TP_BS016 Revision 4
 Effective Date: 01Apr2016

Reference: CS_WI_BS005

Statistical Analysis Plan

- ^a Results of assessments from Visit 7 (Week 4) of Study SEP361-201 will serve as Baseline assessments for the present study. NOTE: Subjects may be hospitalized for the first week of the present study if deemed appropriate by the Investigator.
 - ^b If a subject discontinues from the study, all Visit 11E procedures should be performed at the discontinuation visit, within 48 hours of last study dose.
 - ^c All subjects will have a safety follow-up visit 7 (\pm 2) days after their last dose of study drug.
 - ^d All study drug will be taken once daily in the evening by mouth.

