6.4. RETESTS, UNSCHEDULED VISITS AND EARLY TERMINATION DATA

In general, for by-visit summaries, data recorded at the scheduled visits will be presented.

Unscheduled measurements will not be included in by-visit summaries. Unscheduled measurements collected prior to the first dose of study medication in study 361-201 will contribute to the derivation of the DB baseline value. Unscheduled measurements collected prior to the first dose of extension study medication in study 361-202 will contribute to the derivation of the OL baseline value. Unscheduled measurements collected post OL baseline will contribute to the derivation of the LOCF endpoint, potentially clinically significant (PCS) value, best/ worst case value where required (e.g. shift tables), and identification of a relapse event (see section 16.2.6).

Early termination data collected post OL baseline will be assigned to the next planned visit for that assessment. This mapping will be done for all data points used in the efficacy and safety analyses.

In the case of a retest (same visit number assigned), the latest available measurement for that visit will be used for by-visit summaries.

Listings will include scheduled, unscheduled, retest and early termination data.

Document: Documentation\SAP

Author:

Version Number:
Version Date:

Final V1.0
27FEB2019

Template No: CS_TP_BS016 Revision 4
Effective Date: 01Apr2016

Reference: CS_WI_BS005

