16.2.6. RATE OF RELAPSE AND TIME TO RELAPSE

Subjects demonstrating a relapse of psychotic symptoms during the OL extension treatment period will be identified on the relapse population.

Relapse is defined as the earliest occurrence of any of the following:

- An increase in PANSS total score by $\geq 30\%$ from the PANSS total score at clinical response and a CGI-S score ≥ 3

Document: Documentation\SAP

Author:

Version Number:

Final V1.0

Version Date:

27FEB2019

Template No: CS_TP_BS016 Revision 4
 Effective Date: 01Apr2016

Reference: CS_WI_BS005

Copyright © 2009, 2010, 2012, 2016 Quintiles Transnational Corp. All rights reserved.

The contents of this document are confidential and proprietary to Quintiles Transnational Corp. Unauthorized use, disclosure or reproduction is strictly prohibited.

- Re-hospitalization for worsening of psychosis
- Emergence of suicidality, homicidality, and/or risk of harm to self or others

PANSS and CGI-S assessments taken at both scheduled and unscheduled visits will be considered when identifying the relapse event. Occurrence of re-hospitalization for worsening of psychosis will be identified by medical review of the data collected on the Psychiatric Hospitalization CRF page as well as the SAEs prior to database lock. Emergence of suicidality, homicidality, and/or risk of harm to self or others will be identified as outlined in Appendix 3. The evaluation period for relapse will be from the day/time of clinical response to 1 day after the day of the last dose of extension study medication.

The date of relapse is defined as the earliest of: the date of the assessment (based on the QSSTDTC variable in Bracket data) at which the qualifying PANSS and CGI-S data were collected, the date of hospital admission for worsening of psychosis, the date of the assessment (based on the QSSTDTC variable in Bracket data) at which a qualifying C-SSRS event is identified, or the start date of the qualifying adverse event.

The date of clinical response is defined as the date of the PANSS and CGI-S assessments (based on the QSSTDTC variable in Bracket data) which established clinical response.

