Time-to-relapse (in days) is defined as the date of relapse – the date of clinical response + 1. Subjects completing/discontinuing from the study without meeting the criteria for relapse will be censored on the day after the last dose of extension study medication. Kaplan-Meier estimates of the median time-to-relapse and the 25th percentile and 75th percentile of time-to-relapse, along with the respective 95% confidence intervals, will be calculated. Kaplan-Meier estimate of the probability of relapse at the end of the OL extension treatment period, and its 95% confidence interval, will also be calculated. The time-to-relapse data will be presented in a Kaplan-Meier curve.

The rate of relapse will be calculated as the proportion of subjects demonstrating a relapse during the OL extension treatment period in the relapse population. The 95% confidence interval for the rate of relapse will also be calculated.

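### SAP 6.4 moves an early-termination rating after Visit 4E to Visit 5E with no day limit, so a prior-placebo dropout can enter the relapse population as a 4-week responder with 1 or 0 days at risk

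*SAP*

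**What the plan says.** SAP 5.2 limits the relapse population to "safety population subjects who demonstrated a clinical response to 4 weeks of treatment with SEP-363856". For those who received placebo in 361-201, "clinical response will be evaluated using the Week 4 (Visit 5E) PANSS and CGI-S data of study 361-202", against the double-blind baseline. Protocol 15.3.6.8 fixes the same timing by day: "clinical response will be evaluated using the Day 29 data of study SEP361-202".

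SAP 6.4 states: "Early termination data collected post OL baseline will be assigned to the next planned visit for that assessment". On scope it adds: "This mapping will be done for all data points used in the efficacy and safety analyses". SAP 6.5 applies no visit windows. In SAP Table 1, PANSS and CGI-S are scheduled at every visit from 2E to 11E, so after Visit 4E the next planned visit for both is Visit 5E.

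SAP 16.2.6 dates clinical response by the rating that established it. The evaluation period for relapse runs "from the day/time of clinical response to 1 day after the day of the last dose of extension study medication". Subjects without a relapse "will be censored on the day after the last dose of extension study medication". Time is the end date minus the response date plus 1. The crude rate divides relapses by the whole relapse population.

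For subjects who discontinue, SAP Table 1 note b says "all Visit 11E procedures should be performed at the discontinuation visit, within 48 hours of last study dose". Note d puts dosing in the evening.

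**The concern.** Read in sequence, these rules let an exit rating stand in for the Week 4 rating. A prior-placebo subject who stops soon after Visit 4E while meeting both response criteria becomes a Visit 5E responder. The response date is then the exit visit, which normally falls after the last dose, while the relapse clock stops one day after the last dose.

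Two things are at stake. First, someone who left well short of 4 weeks is labelled a responder to 4 weeks of treatment. Second, someone with essentially no follow-up is counted as not having relapsed. Relapse rate and time to relapse are listed secondary endpoints (protocol 6.2), and the error runs only towards better apparent maintenance of response.

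The point is confined to prior-placebo subjects. Prior SEP-363856 subjects are classified at Visit 7 of 361-201, and inclusion criterion 2 requires them to have completed that study through Week 4.

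**Working it through.** The plan gives no figure to reproduce here. The sample size of about 180 is an anticipated rollover. The check applies the SAP's own date rules.

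**1. Which exits are misclassified on exposure**

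- Visit 4E is Day 22 ± 2 (Days 20 to 24). Visit 5E is Day 29 ± 3 (Days 26 to 32).
- The earliest exit after a Visit 4E is Day 21, so exits on Days 21 to 25 come before the Visit 5E window.
- Let the exit rating fall k calendar days after the last dose. With the first dose on Day 1, exposure in days = exit day − k.
- Exit on Day 21: 20 days (k = 1) or 19 days (k = 2). Exit on Day 25: 24 or 23 days. All are short of 28.
- Exits on Days 26 to 32 fall inside the window. An exit on Day 29 with k = 1 has had 28 days of drug.

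**2. Days at risk**

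Let L be the day of the last dose. The response date is L + k and the censoring date is L + 1, so

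t = (L + 1) − (L + k) + 1 = 2 − k.

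| Exit rating relative to last dose | t (days) |
|---|---|
| same day (k = 0) | 2 |
| 1 day after | 1 |
| 2 days after | 0; the evaluation period ends the day before it starts |
| 3 days after (outside the 48-hour rule) | −1 |

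With evening dosing and a daytime visit, k is normally 1 or 2. For comparison, a responder rated on Day 29 with a last dose on Day 182 and no relapse has t = 183 − 29 + 1 = 155 days.

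**3. Effect on the crude rate**

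With x relapses among R subjects and m added dropouts without a relapse, x/R becomes x/(R + m). For an assumed 20% rate and m = 1:

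- R = 100: 20/101 = 19.8%
- R = 40: 8/41 = 19.5%
- R = 20: 4/21 = 19.0%

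**4. Effect on Kaplan-Meier**

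A record censored at day 0 or 1 is in no risk set from day 2 onward, so it changes no factor of the estimate unless a relapse is dated day 1. In a simulated example (80 subjects, 14 events, first event on day 5), adding 10 such records moved the crude rate from 17.5% to 15.6% and left the Kaplan-Meier estimate at 20.5%.

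**5. How many subjects**

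The documents give none of these inputs. Assume 60 to 90 prior-placebo subjects, 90% still in the study at Visit 4E, 1% to 3% leaving in the following week, and 30% to 50% of those meeting both response criteria.

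- Low: 60 × 0.9 × 0.01 × 0.3 = 0.16
- High: 90 × 0.9 × 0.03 × 0.5 = 1.2

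This counts the whole interval between the two visits. Exits before Day 26 are only part of it.

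**The case against.** The strongest reply is that the plan already excludes these subjects. SAP 5.2 opens with a requirement of 4 weeks of treatment, and a specific population definition can be read as overriding a general mapping rule whose surrounding text is largely about by-visit summaries. SAP 6.5 says data are analysed under the visit recorded on the case report form, and the schedule puts early termination in the Visit 11E column, not Visit 5E. SAP 5 has population membership agreed before database lock, when such a case would be seen.

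Each of these shows intent, but none supplies a rule. The operational test in 5.2 is the Visit 5E data, with no minimum exposure. The mapping in 6.4 is the specific rule for early-termination data and claims all efficacy and safety data points. SAP 17.4.1 applies it to a derived classification, orthostatic events. The pre-lock agreement has no written criterion for this case. At the least, two programmers could build different relapse populations from the same text.

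Other parts of the defence stand. An exit on Days 26 to 32 gives a rating inside the protocol's own Week 4 window. An exit one day after the last dose still leaves that day in the evaluation period, so a qualifying event on it would count. The objective is exploratory and the protocol plans no hypothesis tests.

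**Conclusion.** The gap is real and minor. As written, the plan can admit a prior-placebo dropout rated before Day 26 as a 4-week responder. It also counts dropouts with 1 or 0 days at risk as non-relapsers in the crude rate. The day counts follow from the SAP's formulas alone. The likely number affected, about 0 to 1, and the shift of about 0.2 points per subject rest on the assumed dropout, response, relapse rate and denominator.

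A reader might infer more, and the documents do not support it:

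- **That every re-assigned rating is wrong.** Ratings on Days 26 to 32 are in window, and some follow 28 or more days of drug.
- **That these subjects cannot relapse.** That is strictly true only when the rating comes 2 or more days after the last dose.
- **That the Kaplan-Meier results are distorted.** Records censored this early leave them essentially unchanged.
- **That early termination is the only route to no follow-up.** A subject rated at a true Visit 5E the day after the final dose also gets t = 1.

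**What to change.** Add to SAP 5.2:

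> For subjects who received double-blind placebo, clinical response is established only from PANSS and CGI-S ratings taken within the Visit 5E window (Day 29 ± 3); an early-termination rating re-assigned to Visit 5E under Section 6.4 from before Day 26 does not establish response. Subjects whose response rating falls on or after the day after their last dose have no follow-up after response and are not included in the relapse population.

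The rule turns on study day because one keyed to the early-termination label would discard valid in-window ratings and leave other cases without follow-up in place. The second sentence also removes zero and negative times.

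The cost is a relapse population smaller by about one subject, with no new data and no change to study procedures. Two side effects should be counted before database lock. A scheduled Visit 5E held outside Days 26 to 32 would no longer establish response. A subject with a qualifying event on the single day after the last dose would leave the population with that event.

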6. GENERAL CONSIDERATIONS

6.1. REFERENCE START DATE AND STUDY DAY

Study day will be calculated from the reference start date, and will be used to show start/stop day of assessments and events.

Reference start date is defined as the date of the first dose of study medication of study 361-202 (Day 1).

- If the date of the event is on or after the reference start date then:
 - o Study day = (date of event – reference start date) + 1.
- If the date of the event is prior to the reference start date then:
 - o Study day = (date of event – reference start date).

In the situation where the event date is partial or missing, study day, and any corresponding durations will appear missing in the listings. Partial dates will be however presented as is in the listings.

6.2. BASELINE

Unless otherwise specified, double-blind (DB) baseline is defined as the last non-missing measurement taken prior to the first dose of study medication of study 361-201, including unscheduled assessments. _____

Document: Documentation\SAP

Author:

Version Number:

Final V1.0

Version Date:

27FEB2019

Template No: CS_TP_BS016 Revision 4
 Effective Date: 01Apr2016

Reference: CS_WI_BS005

Copyright © 2009, 2010, 2012, 2016 Quintiles Transnational Corp. All rights reserved.

The contents of this document are confidential and proprietary to Quintiles Transnational Corp. Unauthorized use, disclosure or reproduction is strictly prohibited.

Open-label (OL) baseline is defined as the last non-missing measurement taken prior to the first dose of extension study medication of study 361-202, including unscheduled assessments.

Whenever available, the time information should be accounted for in the derivation of baseline values. In the case where time isn't available and the date of last non-missing measurement and the date of first dose of study medication in study 361-201 or the date of first dose of extension study medication in study 361-202 coincide, that measurement will be considered baseline.

6.3. DERIVED TIME POINTS

The last post OL baseline measurement collected in study 361-202 will be carried forward and will be defined as the last observation carried forward (LOCF) endpoint, using the post OL baseline value up to and including the Week 26 visit data.

The LOCF endpoint will be derived for the following endpoints: PANSS total score, PANSS subscale scores, PANSS five-factor model (Marder) factor scores, PANSS seven-factor model (UPSM) factor scores, CGI-S score, BNSS total score, MADRS total score, AIMS total score, AIMS global severity score (item 8), BARS total score, BARS individual item scores, SAS mean score, PSQI global score, CBB composite score and individual standardized scores of the 4 tests in CBB, UPSA-B total score, and the C-SSRS suicidal ideation score. In addition, the LOCF endpoint will be derived for the following data: vital signs, body weight, BMI, waist circumference, ECG, clinical laboratories, and urine drug screen.

Both scheduled and unscheduled assessments as well as the early termination assessments that are collected post OL baseline will contribute to the derivation of the LOCF endpoint.

6.4. RETESTS, UNSCHEDULED VISITS AND EARLY TERMINATION DATA

In general, for by-visit summaries, data recorded at the scheduled visits will be presented.

Unscheduled measurements will not be included in by-visit summaries. Unscheduled measurements collected prior to the first dose of study medication in study 361-201 will contribute to the derivation of the DB baseline value. Unscheduled measurements collected prior to the first dose of extension study medication in study 361-202 will contribute to the derivation of the OL baseline value. Unscheduled measurements collected post OL baseline will contribute to the derivation of the LOCF endpoint, potentially clinically significant (PCS) value, best/ worst case value where required (e.g. shift tables), and identification of a relapse event (see section 16.2.6).

Early termination data collected post OL baseline will be assigned to the next planned visit for that assessment. This mapping will be done for all data points used in the efficacy and safety analyses.

In the case of a retest (same visit number assigned), the latest available measurement for that visit will be used for by-visit summaries.

Listings will include scheduled, unscheduled, retest and early termination data.

Document: Documentation\SAP

Author:

Version Number:
Version Date:

Final V1.0
27FEB2019

Template No: CS_TP_BS016 Revision 4
Effective Date: 01Apr2016

Reference: CS_WI_BS005

6.5. WINDOWING CONVENTIONS

All data will be analyzed according to the schedule outlined in the CSP and according to the visit denoted on the case report form (CRF). No visit windowing will be performed during the analysis for this study.

6.6. STATISTICAL TESTS

All statistical inference, unless otherwise stated, will be performed with two-sided tests at the significance level of 0.05, and two-sided 95% confidence intervals (CIs) will be calculated whenever appropriate.

